12.6.1.4 Repeats of AE Analyses without Censoring

In the EOT analysis the following outputs are repeated without applying any censoring rules due to subject unblinding or AV receipt:

- Overall summary of unsolicited AEs occurring through 28 days after any dose
- Unsolicited AEs, SAEs, unsolicited AESIs and AEs with fatal outcome, by SOC and PT occurring through EOT Visit

12.6.2 Deaths and Serious Adverse Events

Description of analyses of SAEs and fatal AEs are included in Section 12.6.1.1.

12.6.3 Laboratory Data

A urine sample for pregnancy testing is taken from women of childbearing potential on Day 1 prior to trial vaccination to establish eligibility. A urine pregnancy test is also performed before the second trial vaccination on Day 29 to continue to determine eligibility. Urine pregnancy test result data is listed only.

No other standard laboratory tests are performed.

12.6.4 Vital Signs

Vital signs are recorded at each clinic visit (i.e. Day 1, Day 29, Day 43, Day 57 [Immunogenicity/Reactogenicity Subset only], Day 120 [Immunogenicity/Reactogenicity Subset only], Day 211, and Day 393 / EOT). Body temperature (°C), SBP/DBP (mmHg) and pulse (beats per minute) at baseline and each post-baseline timepoint as well as change from baseline at each post-baseline timepoint is summarized.

Vital Signs data is summarized based on the SAS.

12.6.5 Physical Examinations, ECGs, and Other Observations Related to Safety

General physical examinations are performed at Day 1 and Day 393 / EOT. Symptom-directed examinations are performed Day 29, Day 43, Day 57, Day 120, and Day 211. Physical examination data is listed only.

12.6.6 Sensitivity Analysis on Safety Outputs

For the safety delivery when the first 1037 subjects are 6 weeks post 2nd vaccination all safety outputs are repeated without applying any censoring due to AV-prone subject use or unblinding.

12.6.7 Adapting the Safety Analyses to the Requirements of Extensive Unblinding

If not explicitly exempted, all safety analyses described in Sections 12.6.1 – 12.6.6 are performed under the conditions of data censoring (described in Section 10.10).

In order to maximally maintain the previous analysis setup while nevertheless aiming at optimally evaluating the collected data the following approach is introduced regarding safety analyses.

1. The above-mentioned analyses (Sections 12.6.1 – 12.6.6) remain unchanged, regardless of extensive unblinding. All definitions still correctly apply and analyses are conducted as originally planned and described above.
2. Additional outputs are planned to account for the massive loss of data due to censoring. The concerned analyses are explicitly listed at the end of this Section 12.6.7.
 - a. These additional outputs are closely following the above mentioned safety analyses.
 - b. As far as possible, endpoint definitions and analysis sets are maintained as described in Sections 12.6.1 – 12.6.6.
 - c. No censoring due to unblinding and/or AV receipt is performed.
 - d. AEs/vital sign values are divided into 4 groups: Placebo-only, CVnCoV-only, CVnCoV-AV, AV-only.

AEs/vital sign values are allocated to treatment groups as follows:

- Placebo-only: Only placebo has been administered before AE start date / vital signs date. No CVnCoV and no AV must have been administered until then.

- CVnCoV-only: At least one dose of CVnCoV and no AV has been administered before AE start date / vital signs date. Placebo might have been administered as well.
- CVnCoV-AV: At least one dose of CVnCoV and at least one dose of AV has been administered before AE start date / vital signs date. Placebo might have been administered as well.
- AV-only: At least one dose of AV and no CVnCoV has been administered before AE start date / vital signs date. Placebo might have been administered as well.

Treatments are considered “as received”, not “as randomized”.

The following analyses are repeated as described above. All repeat analyses are based on the SAS.

- Overall summary of unsolicited AEs occurring through EOT Visit
- Unsolicited AEs, SAEs, unsolicited AESIs and AEs with fatal outcome, by SOC and PT occurring through EOT Visit

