--	--

	
The final analysis data from the HERALD study (CV-NCOV-004), conducted with the same study vaccine (CVnCoV) was made available on the 30th June 2021. The HERALD study results were statistically significant for the primary study objective. The final efficacy analysis showed an overall efficacy of 48.2% (LL (lower limit) 31,0%) for CVnCoV in the prevention of COVID-19 cases of any severity, reaching the predefined success criterion. Similar confirmatory results were observed in the prevention of moderate to severe COVID-19 cases, a key secondary efficacy objective, with an overall vaccine efficacy of 70.7% (LL 42.5%).
 
Whereas, in the HERALD study, CVnCoV efficacy in the prevention of COVID-19 cases of any severity was confirmed in the 18 to 60 age group (VE 52.5%, LL 36.2%), data in study participants older than 60 years was not conclusive including due to the low number of cases (only 9% of all cases) and low number of participants under follow up in that age group. There was also no clear trend of efficacy in this age group. Similarly, vaccine efficacy in the prevention of moderate to severe disease was 77.2% (LL 51.8%) in participants 18 to 60 years old and no conclusive results were observed in participants older than 60 years.
 
Since the efficacy results from the HERALD study for CVnCoV are available and all subjects in the CV-NCOV-005 study are currently eligible to receive an authorized vaccine, all subjects in this CV-NCOV-005 study will be unblinded.
 
Each subject will be informed by the study physician of the available study results and whether he/she received the study vaccine (CVnCoV) or placebo in the study. The purpose of this measure is to provide the participants/subjects with sufficient information so that they can decide whether to take an authorized vaccine or not in a fully informed way.
 
All subjects that received placebo in this study should follow the official recommendations regarding vaccination against SARS-CoV-2 outside of the study; no further follow up will be required and the subjects will leave the study.
 
The subjects that received at least one dose of CVnCoV and already decided to take an authorized vaccine, will be asked to remain in the study to allow safety follow-up:
 
Since for subjects older than 60 years, a favorable benefit-risk for CVnCoV could not be established based on the HERALD study results, subjects who received CVnCoV should follow the official recommendations regarding vaccination against SARS-CoV-2 outside of the study.
 
Subjects 60 and younger willing to take the authorized vaccine should inform the site and are encouraged to speak with the study doctor/ investigator for further information on the CVnCoV final efficacy analysis results and how to access the authorized vaccine, out of the clinical study setting.
 
All subjects receiving the authorized vaccine following at least one dose of CVnCoV should continue the safety follow-up in the study until the end of the trial (Schedule of Activities- Table 2).
 
To date, no clinical trial has proactively investigated or been designed to evaluate the administration of authorized vaccines after vaccination with CVnCoV.
 
A post-hoc analysis in June 2021 showed that 438 participants across CVnCoV studies were administered authorised COVID-19 vaccine through national vaccination programmes after having received one or two 12µg-doses of CVnCoV during clinical studies. The most frequent authorised

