### **7.6.2 Prohibited Medications/Vaccines During the Trial**

- Use of any investigational or non-registered product (vaccine or drug) is prohibited during the trial.
- Authorized SARS-CoV-2 vaccines are allowed. An interval of at least 21 days should be observed between the last dose of CVnCoV and the authorized vaccine.
- Other licensed vaccines should not be administered within 28 days (for live vaccines) or 14 days (for inactivated vaccines) of trial vaccine administration during the trial.
- Receipt of any other investigational SARS-CoV-2 vaccine or vaccines against other virus from the coronavirus family is prohibited during the trial.
- Any treatment with immunosuppressants or other immune-modifying drugs (including but not limited to corticosteroids, biologicals and methotrexate) is prohibited during the trial. For corticosteroid use, this means prednisone or equivalent, 0.5 mg/kg/day for 14 days or more. The use of inhaled, topical, or localized injections of corticosteroids (e.g., for joint pain/inflammation) is permitted.
- Administration of immunoglobulins or any blood products is prohibited during the trial.

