10.5.4 Unsolicited AEs

Information on unsolicited AEs occurring on each vaccination day (i.e. dose 1 and 2) and the following 28 days after each dose is collected for subjects in the Immunogenicity/Reactogenicity subset. Data is recorded in the eDiary by the subject to aid AE reporting. The investigator reviews the eDiary and records information on any AEs on the CRF.

Unsolicited AEs are assigned to first or second dose based on the (reported or imputed) AE date. Unsolicited AEs occurring before dose 2 are assigned to dose 1. Unsolicited AEs occurring after dose 2, are assigned to dose 2. Unsolicited AEs occurring on the day of dose 2 are assigned to either dose 1 or dose 2 as per the following rules:

- If the AE occurred on the day of dose 2 but before vaccination with dose 2, the AE is assigned to dose 1
- If the AE occurred on the day of dose 2 but on or after vaccination with dose 2, it is assigned to dose 2.
- If the AE occurred on the day of dose 2 and it cannot be determined whether it occurred before, on or after vaccination with dose 2, it is assigned to dose 2.

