10.5.8 Overreported AEs

The definition of overreported AEs consists of the following 6 items:

No overreporting restrictions exist for:

1. (Treatment emergent) AESIs
2. (Treatment emergent) SAEs
3. (Treatment emergent) non-serious intercurrent medical condition that may affect the immune response to vaccination
4. (Treatment emergent) AEs leading to vaccine withdrawal or trial discontinuation

Overreporting restrictions:

5. Medically attended TEAEs not matching any of the above 4 categories that have started later than 6 months after 2nd dose
6. TEAEs not matching any of the above 5 categories that have started later than 28 days after any dose. (I.e. An AE starting between Day 29 and 49 when dose 2 was given on Day 50 is also an overreported AE.)

In the output, overreported AEs are displayed in listings but are not included in tables.

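### SAP 12.6.7 sets unsolicited AEs through end of trial side by side in four exposure groups, although ordinary unsolicited AEs are barely collected after an authorized vaccine, so the AV columns understate that class

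*SAP*

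**What the plan says.** SAP 12.6.7 adds safety outputs because censoring removes much of the data. In these outputs "AEs/vital sign values are divided into 4 groups: Placebo-only, CVnCoV-only, CVnCoV-AV, AV-only", according to what was given before the event started, and "No censoring due to unblinding and/or AV receipt is performed". The repeated outputs, all on the SAS, are an "Overall summary of unsolicited AEs occurring through EOT Visit" and SOC/PT tables of unsolicited AEs, SAEs, unsolicited AESIs and fatal AEs through EOT. The section states no caveat on ascertainment and no denominator or person-time per exposure group.

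Collection is narrower. SAP 10.5.4: "Information on unsolicited AEs occurring on each vaccination day (i.e. dose 1 and 2) and the following 28 days after each dose is collected", for subset subjects only. SAP 10.5 gives the classes recorded in all subjects: medically attended AEs to 6 months after dose 2; SAEs, AESIs and AEs leading to withdrawal to EOT; and intercurrent conditions throughout. It says nothing else needs recording.

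SAP 10.5.8 restricts the tables in the same way. Its residual category is "TEAEs not matching any of the above 5 categories that have started later than 28 days after any dose", and "In the output, overreported AEs are displayed in listings but are not included in tables". Medically attended AEs leave the tables 6 months after dose 2. SAEs, AESIs, intercurrent conditions and AEs leading to withdrawal have no limit.

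On AV, Protocol 7.6.2 says "An interval of at least 21 days should be observed between the last dose of CVnCoV and the authorized vaccine". Protocol 2 and 9.1.2 move subset subjects who take an AV after CVnCoV to Table 2 from the day of the AV. Table 2 has no row for unsolicited AEs.

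**The concern.** The four columns are formed by exposure at the time of the event, but the collection rules follow the trial doses and do not restart at the AV. The Placebo-only and CVnCoV-only columns therefore contain the diary-supported reporting periods. The CVnCoV-AV and AV-only columns consist mostly of later follow-up, in which ordinary unsolicited AEs are neither requested nor tabulated.

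This matters most for CVnCoV-AV. According to the protocol synopsis, CVnCoV recipients who chose an AV "will be asked to remain in the study to allow safety follow-up", and no trial had been designed to evaluate an AV given after CVnCoV. A lower count of ordinary AEs in that column could be read as a safety finding when it only reflects what was collected.

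**Working it through.** The plan gives no figure on this point, so there is none to reproduce. The check counts the days after an AV on which a newly starting AE can still enter the tables.

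**Inputs**
- Ordinary AEs: dose day plus 28 days after each trial dose (SAP 10.5.4, 10.5.8).
- Medically attended AEs: start date − dose 2 date + 1 ≤ 180, so up to 179 days after dose 2 (SAP 10.5.6).
- SAEs and AESIs: through Day 393, which is dose 2 + 364 days (Protocol Table 1 and Table 2).
- Doses on Day 1 and Day 29.
- AV given k days after dose 2. The documents give no AV dates, so k is an assumption and is shown as a range.

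**Total collection time for ordinary AEs.** Days 1–29 and Days 29–57 share Day 29: 29 + 29 − 1 = 57 days.

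**Days after AV.** SAP 12.6.7 requires the AV to precede the event, so the count is max(0, L − k), with L = 28, 179 or 364.

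| k (days from dose 2 to AV) | Ordinary | Share of 57 | Medically attended | SAE/AESI |
|---|---|---|---|---|
| 0 | 28 | 49% | 179 | 364 |
| 14 | 14 | 25% | 165 | 350 |
| 21 | 7 | 12% | 158 | 343 |
| 28 | 0 | 0% | 151 | 336 |
| 60 | 0 | 0% | 119 | 304 |
| 120 | 0 | 0% | 59 | 244 |
| 179 | 0 | 0% | 0 | 185 |

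**Equal true rates.** Let the daily rate of ordinary AEs be λ before and after AV. With k = 21, a subset subject contributes 50λ expected events to CVnCoV-only (Days 1–50) and at most 7λ to CVnCoV-AV, although 343 days of follow-up remain after the AV. Dividing by that follow-up gives 7λ/343 = 0.02λ, against λ before the AV. Person-time through EOT therefore does not repair this class, because the missing events were not collected.

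**Effect of Table 2.** The ordinary column is an upper limit set by the tabulation rule. For CVnCoV recipients moved to Table 2 at the AV, routine collection stops that day, even inside the 28 days. This change of schedule came with protocol version 3.0, so earlier AV recipients may differ.

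**Other classes.** With k = 21, medically attended AEs have 50 days before the AV (Days 1–50) and 158 after it. SAEs and AESIs have 50 and 343. For these classes the imbalance in time runs the other way.

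**The case against.** The strongest reply is that the AV columns are far from empty. SAP 12.6.1 counts SAEs and AESIs among unsolicited AEs. SAP 10.5.8 leaves four classes without a limit and keeps medically attended AEs to 6 months, and SAP 12.6.1.1 says the all-reported summaries include events later than 28 days. The 12.6.7 outputs are descriptive extras beside unchanged censored analyses, and no safety testing is planned.

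Much of this stands. A reader might infer that the AV columns contain no unsolicited AEs by design, or that the table as a whole must show fewer AEs after AV. The documents support neither. Only the ordinary class is cut off, and for medically attended AEs, SAEs and AESIs an early AV leaves more time after it than before it.

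A reader might also take 7 days as a ceiling. It is not one. The 21-day interval is a recommendation and is stated only after CVnCoV, so it does not bound AV-only. SAP 9.5.5 and 12.1 foresee AV within 15 days of dose 2 and before dose 2. Nor do all subjects have the collection windows: only the first 1,260 of about 2,520 do, and the others contribute no routinely collected ordinary AEs to any column.

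The reply does not rescue the comparison for ordinary AEs. If SAP 10.5.8 governs, late ordinary AEs are not tabulated. If the wording of 12.6.1.1 governs, the AV columns hold only chance reports, because Protocol 9.1.1.6 tells subjects at Day 57 that unsolicited reporting is complete. The descriptive purpose does not help either: side-by-side columns will be compared.

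**Conclusion.** The point holds for ordinary unsolicited AEs. Their ascertainment differs between the trial-vaccine-only and AV columns, and with equal true rates the AV columns show fewer. After AV at most 14 of 57 collection days remain if AV follows dose 2 by 14 days, 7 if by 21 days, and none from 28 days on. For CVnCoV recipients already on Table 2, none remain at any interval.

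For all unsolicited AEs combined, the net direction is not determined by the documents. It depends on AV timing and on the mix of event classes, so the plan cannot be said to guarantee a reassuring table.

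The result assumes on-schedule doses and reads the dose in SAP 10.5.8 as a trial dose, as that section's dose 2 example suggests. If AV doses also counted, late events would not be barred from tables for 28 days after an AV, but collection would still not extend to them. The change should be made before the final tables are produced.

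**What to change.** In SAP 12.6.7:

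- Take ordinary unsolicited AEs out of the four-group overall summary and out of the four-group SOC/PT table. List those starting after AV, with a footnote that this class was not systematically collected after AV.
- Keep SAEs, AESIs, fatal AEs and AEs leading to withdrawal through EOT, and medically attended AEs within their 6-month window. These are collected after AV and should not be dropped or footnoted as uncollected. Intercurrent conditions can stay on the same terms.
- Give person-time at risk per exposure group for each retained class. Placebo subjects are withdrawn after unblinding (Protocol 5.1, 8.2), and time before and after AV differs between subjects.
- State that SAP 10.5.8 takes precedence over the all-reported wording of 12.6.1.1 for these tables.

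The cost is SAP wording and the derivation of person-time by exposure group and class. The downside is that incidental ordinary AEs after AV appear only in the listing.

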12.7 Immunogenicity Analyses

For subjects in the Immunogenicity/Reactogenicity Subset, blood samples for SARS-CoV-2 viral neutralizing activity and antibody to SARS-CoV-2 RBD of S protein testing are collected on Day 1, Day 29 and Day 43.

In general, all analyses of SARS-CoV-2 RBD to S protein antibodies and SARS-CoV-2 viral neutralizing antibody levels are performed based on the PPI, for the pooled CVnCoV lots, split by lot and for placebo, and separately in subjects seronegative to the N protein at baseline and in subjects seropositive to the N protein at baseline (see Section 10.6.1). Summary statistics presented include the Geometric Mean (GM) with corresponding geometric SD and 95% CI, as well as the Median, Min, Max, Q1 and Q3.

Total columns (or respective sections in graphs) are not provided for immunogenicity outputs.

12.7.1 Primary Immunogenicity Analyses

SARS-CoV-2 RBD of S protein antibodies (expressed as GMT) are summarized descriptively. Summaries are provided at baseline and each post-baseline sampling timepoint. The fold change (FC) from baseline is further computed and summarized for Day 29 and Day 43.

For each post-baseline timepoint, the number and percentage of subjects seroconverting with any fold increase, a 2-fold increase and a 4-fold increase are presented together with the exact 95% Pearson-Clopper CIs for the proportion of seroconverting subjects. This analysis is only done for subjects seronegative to the N protein at baseline. For a definition of seroconversion for subjects seronegative at baseline, see Section 10.6.2.

GMTs of SARS-CoV-2 RBD of S protein antibody levels over time are presented in the following figures:

- Line plot of GM FC from baseline and 95% CIs,
- Line plot of GMTs with GM and 95% CIs,
- Boxplots of GMTs with median, Q1 and Q3, and whiskers representing minimum and maximum by vaccine group.

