### **10.3.6 Immunogenicity Analysis**

No formal hypothesis on immunogenicity will be tested. Descriptive statistics for the immunogenicity endpoints will be provided for a subset of subjects for each CVnCoV lot separately (n = 100 per lot), for pooled lots and for a subset of subjects in the placebo group (n = 50) on Days 1, 29 and 43.

The following analyses will be done for SARS-CoV-2 RBD of the S protein antibody concentrations and for neutralizing antibodies titers :

- Geometric mean concentrations (GMC) / geometric mean titers (GMT) by group will be summarized with their 95% CI at blood sampling time points Day 1, Day 29 and Day 43 for 250 evaluable subjects and then separately in subjects seronegative at baseline and in subjects seropositive at baseline.
- The fold change from baseline will be computed for seropositive subjects at baseline and GMFC by group will be displayed with their 95% CI at the Day 29 and Day 43 blood sampling time point.
- The number and percentage of subjects SARS-CoV-2 seronegative at baseline for whom a seroconversion is observed will be summarized and presented at each blood

sampling time point after baseline until Day 43 with exact 95% CI. Seroconversion is defined as detectable antibodies in the serum ( $\geq$  lower limit of quantification (LLOQ)).

Concentrations/titers marked as below the LLOQ will be arbitrary replaced by half of the LLOQ for GMC/GMT and GMFC computations purpose.

To assess lot-to-lot consistency, the two-sided 95% CI of the ratio of GMCs of SARS-CoV-2 RBD of S protein antibodies between subjects receiving 2 different lots of CVnCoV will be computed for Day 43.

Additional immunogenicity analyses including graphs will be described in SAP as applicable.

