10.3 Missing Data

In general, no imputation of missing values is done except for the following:

- Imputation of missing onset date for confirmed COVID-19 cases as specified in Section 10.7.2.
- For SARS-CoV-2 RBD of S protein antibodies, and viral neutralizing antibodies, concentration values marked as below the lower limit of quantification (LLOQ) are set to 0.5*LLOQ for computation purposes.
- Imputation of (partially) missing AE start dates:
 - If start date year value is missing, the date uncertainty is too high to impute a rational date. Therefore, if year value is missing, the imputed AE start date is set to missing.
 - If start date year value is before the vaccination start date year value, then the AE started before the vaccination. Therefore:
 - If month is missing, the imputed start date is set to the mid-year point (i.e., 01JULYYYY).
 - If month is not missing, the imputed start date is set to the mid-month point (i.e., 15MONYYYY).
 - If start date year value is equal to the vaccination start date year value, the start date month needs to be compared against the vaccination start date month, to determine the imputation rule to apply. Therefore:
 - If month is missing, the imputed month and imputed day is the same as start of vaccination
 - If month is lower than vaccination start date month and start date day is missing, the imputed start date is set to the mid-month point (i.e. 15MONYYYY).
 - If month is equal to the vaccination start date month and start date day is missing, the start day is set to the start day of vaccination.
 - If month is greater than the vaccination start date month and start date day is missing, the imputed start date is set to the beginning of the month (i.e., 01MONYYYY).
 - If start date year value is greater than the vaccination start date year value, the AE started after vaccination. Therefore:

- If month is missing, the imputed start date is set to the year start point (i.e., 01JANYYYY).
- If start date month is not missing and start date day is missing, the imputed start date is set to the beginning of the month (i.e., 01MONYYYY).
- If after imputation of start and resolution date (see below) a start date is after the resolution date (for example if a missing day of a start date is set to 15 and the resolution date is before the 15th of the same month and year) then the start date is set to the resolution date.
- Imputation of (partially) missing AE end dates:

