10.6 Immunogenicity Assessments

Immunogenicity assessments are only performed in subjects from the Immunogenicity/Reactogenicity Subset to assess the immune response induced by vaccination with CVnCoV and are evaluated in 2 ways:

- Binding antibodies to the SARS-CoV-2 RBD of the S protein (IgG) measured in serum by immunoassay.
- Viral neutralizing antibodies directed against SARS-CoV-2 (MN 25 TCID50) measured in serum by a functional activity assay.

Results from the two assays are quantitative. Measures below the LLoQ are presented as half the LLoQ in the data.

Further assessments for serology status to natural SARS-CoV-2 infection (SARS-CoV-2 N protein) are performed in all subjects by immunoassay. The N protein is not a component of the CVnCoV vaccine, but is measured to determine the serostatus of subjects to the SARS-CoV-2 virus and the occurrence of SARS-CoV-2 infections during the trial (see also Section **Error! Reference source not found.**). Data provided is qualitative (positive/negative).

As the immunogenicity results would potentially unblind the subject's treatment assignment, the laboratory performing the assays keeps the results in strict confidence. The SARS-CoV-2 N protein data is not considered unblinding information.

After approval of protocol v3.0 immunogenicity assessments are no longer performed.

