10.6.2.1 SARS-CoV-2 RBD of S Protein Antibodies

In subjects who tested seronegative to the N protein for SARS-CoV-2 at baseline (see Section 10.6.1), seroconversion is defined as a fold increase above 1 in antibody titer against SARS-CoV-2 RBD of S protein.

In subjects who tested seropositive to the N protein for SARS-CoV-2 at baseline (see Section 10.6.1), the definition for seroconversion is a fold increase above 2 in antibody titer against SARS-CoV-2 RBD of S protein versus baseline.

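### In subjects below LLOQ at baseline, the SAP's 2-fold and 4-fold rows and absolute fold change are set by the LLOQ/2 substitution, in an undeclared widening of the protocol's fold-change scope

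*SAP*

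**What the plan says.** SAP 12.7.1, on the primary (RBD) endpoint: "The fold change (FC) from baseline is further computed and summarized for Day 29 and Day 43". SAP 12.7 requires the immunogenicity analyses "separately in subjects seronegative to the N protein at baseline and in subjects seropositive to the N protein at baseline", so fold change is also produced in the N-seronegative stratum. The line plot of geometric mean fold change carries no restriction either. The responder table gives subjects "with any fold increase, a 2-fold increase and a 4-fold increase are presented", and "This analysis is only done for subjects seronegative to the N protein at baseline". For these subjects SAP 10.6.2.1 says "seroconversion is defined as a fold increase above 1 in antibody titer against SARS-CoV-2 RBD of S protein". SAP 12.7.2 repeats all of this for neutralizing antibodies.

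On low results, SAP 10.6 says "Measures below the LLoQ are presented as half the LLoQ in the data", and SAP 10.3 says that values below LLOQ "are set to 0.5*LLOQ for computation purposes".

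Protocol 10.3.6 is narrower: "The fold change from baseline will be computed for seropositive subjects at baseline". The estimands in Protocol 4.3 agree. Geometric mean fold change is for baseline seropositives; seronegatives get geometric means and seroconversion, which 10.3.6 defines as a result at or above LLOQ. The protocol has no 2-fold or 4-fold rows. SAP 6.1 lists 17 changes from protocol and the wider fold-change scope is not among them. The SAP estimand table (9.4) has no fold-change entry.

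**The concern.** Subjects with known positive serology are excluded at entry (exclusion criterion 1), although Protocol 5.2 says not every entrant is screened. The N-seronegative stratum should therefore consist mainly of subjects below LLOQ at baseline in the RBD and neutralization assays. Their fold change has a substituted constant, not a measurement, as its denominator.

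A reader who sees three rows of rising stringency will take them as three different facts, and will take a 4-fold increase as a rise of at least that size. If the denominator is a constant fraction of LLOQ, the rows are only cut-offs on the later titre, and two of the three may coincide. These rows describe the primary and the secondary immunogenicity endpoints.

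**Working it through.** The plan gives no figure to reproduce: there is no power, margin or expected titre for these outputs, and no LLOQ value. Results are therefore in units of the LLOQ, written L.

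**Inputs.** Baseline below LLOQ is recorded as L/2 (SAP 10.3, 10.6). A later value below LLOQ is also L/2. Fold change FC = later value ÷ baseline.

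**1. What each row means when baseline is below LLOQ.**

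| Later value | FC | Any (> 1) | ≥ 2 | ≥ 4 |
|---|---|---|---|---|
| below L (recorded 0.5 L) | 0.5/0.5 = 1 | no | no | no |
| L | 1/0.5 = 2 | yes | yes | no |
| 1.5 L | 1.5/0.5 = 3 | yes | yes | no |
| 2 L | 2/0.5 = 4 | yes | yes | yes |

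No FC between 1 and 2 can occur. FC > 1, FC ≥ 2 and a later value ≥ L are the same event; FC ≥ 4 is the same event as a later value ≥ 2 L.

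**2. Size for the responder rows.** Assume lognormal later titres with log10 SD 0.4 (not in the documents) and all baselines below LLOQ. Then P(value ≥ kL) = Φ(log10(GMT/kL)/0.4).

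| GMT | 2-fold as written (k = 1) | 4-fold as written, or 2-fold against L (k = 2) | 4-fold against L (k = 4) |
|---|---|---|---|
| 2 L | 77% | 50% | 23% |
| 4 L | 93% | 77% | 50% |
| 8 L | 99% | 93% | 77% |

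**3. Size for the geometric mean fold change.** If all baselines are L/2, it equals GMT ÷ (L/2). In a simulation of the same sera (assumed lognormal, GM 8 units, natural-log SD 1.2) with LLOQ set to 0.5, 1, 2, 4 and 8 units, it came out at 31.7, 15.8, 7.9, 4.0 and 2.3. At LLOQ = 1, substituting LLOQ instead of LLOQ/2 changes 15.8 to 8.1.

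**4. Direction of error.** With true baseline b < L and a quantifiable later value, recorded FC ÷ true FC = b ÷ (L/2) = 2b/L. This exceeds 1 if b is between L/2 and L, and is below 1 if b is under L/2. The documents give no distribution below LLOQ, so the net direction is unknown.

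**5. Between groups.** With baseline L/2 in both groups, the ratio of mean fold changes equals the ratio of GMTs: the baseline constant cancels. Only later values below LLOQ keep some dependence on the floor.

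**6. How far the identities carry to the table.** The rows cover N-seronegatives, some of whom may have quantifiable RBD or neutralizing antibody at baseline. In a simulation with an assumed 2%, 5% or 10% of such subjects, the any-fold and 2-fold rows were 82.1 v 81.0%, 82.0 v 79.4% and 81.7 v 76.6%.

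**7. ≥ or >.** SAP 12.7.1 does not say, and SAP 10.6.2 uses a strict threshold of 2 for N-seropositives. Under a strict reading a value exactly at LLOQ fails the 2-fold row. For titres on two-fold dilution steps (an assumption; simulated with LLOQ 10, log2 mean at 20, SD 1.3 steps, rounded down), any-fold and ≥ 2 were both 78.0%, while > 2 and ≥ 4 were both 50.0%.

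**The case against.** Protocol 10.3.6 closes by leaving further immunogenicity analyses and graphs to the SAP, and it does not forbid fold change in seronegatives. A reader might infer a protocol breach; the documents support only an addition that SAP 6.1 does not list. That answer stands.

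A reader might infer that the seroconversion endpoint is distorted. It is not, for subjects below LLOQ at baseline: the any-fold row then equals the protocol's own definition, a result at or above LLOQ. The 2-fold row beside it is redundant, not false. Assay noise that carries a titre across LLOQ would count under the protocol's rule too, so LLOQ/2 does not cause it.

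A reader might also infer that fold rises are systematically overstated. Step 4 shows that this is not established: for a truly naive subject with a level well below LLOQ/2, the recorded fold change understates the rise. A placebo subject below LLOQ on both days has FC = 1.

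Nor is LLOQ/2 itself a departure. Protocol 10.3.6 applies it to mean fold change as well as to geometric means; its restriction to baseline seropositives is what largely avoids the problem.

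Finally, no immunogenicity hypothesis is tested, the LLOQ/2 rule is stated, and GMTs with intervals and quartiles accompany the fold changes. SAP 12.0 adds that some described analyses were never performed and refers to Appendix 4, which is held outside the SAP, so the documents do not show whether these outputs are in the final set. All this limits the consequence. It does not make a 4-fold row that needs only 2 × LLOQ mean what its label says.

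**Conclusion.** The point holds for subjects below LLOQ at baseline in the assay analysed, with thresholds read as ≥. For them the 2-fold row repeats the any-detectable row, the 4-fold row is a cut at 2 × LLOQ, and the absolute geometric mean fold change depends on the assay floor. Across the N-seronegative table the rows coincide only approximately if some subjects have quantifiable baselines. That most are below LLOQ is an expectation from the entry criteria, not a figure in the documents.

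Under the assumed SD, the choice of reference moves the 4-fold percentage by 16 to 27 points (93% v 77%; 77% v 50%; 50% v 23%). The outputs are descriptive, so no error rate or sample size changes, and lot and vaccine-placebo comparisons of mean fold change are largely unaffected. What remains is a labelling and interpretation problem in the primary and secondary immunogenicity outputs, with a widened scope that SAP 6.1 should have listed. It is worth correcting because the correction is cheap.

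**What to change.** 1. In SAP 12.7.1, for a subject below LLOQ at baseline in that assay, count the 2-fold row only if the later value is ≥ 2 × LLOQ and the 4-fold row only if it is ≥ 4 × LLOQ. Since the true baseline is below LLOQ, each row then guarantees the measured rise it names. State ≥ explicitly for all rows.
2. Report the geometric mean fold change and its plot for subjects with baseline ≥ LLOQ in that assay, keeping LLOQ/2 for their later values below LLOQ as Protocol 10.3.6 provides. That section does not name the antibody that defines seropositivity; Protocol 10.2.3 uses the antibody being analysed for seroconversion, so the assay-specific reading is consistent with it. If fold change is kept for the other subjects, list the wider scope in SAP 6.1 and label the output as relative to LLOQ/2.
3. Carry the same wording into 12.7.2.

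SAP 6.0 states that version 4.0 was written and approved by an unblinded team, and SAP 8.2 places a first immunogenicity delivery in August 2021. Show the new rows beside those now specified and mark them as added, so that the change cannot be read as selective.

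Cost: a few sentences and a small programming change, with no new data. The 2-fold and 4-fold percentages become lower and conservative, and for subjects with true levels well below LLOQ/2 they understate the rise further.
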